## 11.2 Anticipated adverse device effects in the clinical investigation

The identified risks for the investigational device are described in the investigator’s brochure. The table below lists risks anticipated adverse device effects in the current clinical investigation.

| Problem                          | Affects         | Caused by        | Subject withdrawn | Solution   |
|----------------------------------|-----------------|------------------|-------------------|--|
| No iDAScore calculated           | Treatment group | Technical issues | Yes               | Conventional morphology is used to select an embryo for transfer.  |
| Highest scoring embryo overruled | Treatment group | iDAScore ranking | Yes               | Conventional morphology is used to select an embryo for transfer.  |
| No pictures of embryos           | Both groups     | Technical issues | Yes               | Culture dish is removed from the incubator and conventional morphology is assessed using an external microscope. |

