#### **14.7 Efficacy analyses**

The primary statistical analysis will be calculation of the mean percentage difference with 95% confidence interval (CI) regarding pregnancy rate between the iDA group and the trained embryologist group. If the lower limit of this 95% CI exceeds -5%, the non-inferiority margin, then non-inferiority is achieved. If non-inferiority is achieved, then we could test for superiority which means that the lower limit of the above 95% CI will be greater than zero. This analysis will be applied on the PP population (primary) and ITT population (sensitivity analysis). Any inconsistencies in these analyses will be discussed in the study report.

The primary analysis will also be performed adjusted by center and performed per center. If baseline confounders are found the adjusted analyses will be performed adjusted for these variables.

The secondary efficacy analyses will be the comparison between the two randomized group regarding the secondary outcome variables given in section secondary outcomes.

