2 STUDY POPULATIONS

Definition of Study Populations

2.1.1 *Intent-to-Treat Population*

All randomized subjects will be included in the Intent-to-Treat (ITT) population. Subjects will be analysed according to randomized group.

2.1.2 *Full Analysis Set*

All randomized subjects with measurement of primary efficacy variable will be included in the Full Analysis Set (FAS). Subjects will be analysed according to randomized group.

2.1.3 *Per-Protocol Population*

All randomized subjects with no significant protocol violations will be included in the Per Protocol (PP) population. Subjects will be analysed according to actual embryo selection method. The Per Protocol population will be defined during the clean file meeting before the database lock without knowledge to which randomised group the patient belongs to.

2.1.4 *Safety Population*

All enrolled subjects who started one of the study embryo selections methods (i.e., in patients with a minimum of two early blastocysts) will be included in the safety population.

The final decisions regarding all the above study population will be taken at the Clean File meeting before the database lock.

STATISTISKA KONSULTGRUPPEN		Statistical Analysis Plan	
Protocol:		Protocol No: <protocol number>	
eValuating iDA Selection Ability. The VISA study.		Version: 2.0	Page 11 of 25

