Mantel-Haenszel chi-square test for ordered categorical variables and

Pearson chi-square test for non-ordered categorical variables.

Dichotomous data will be expressed as numbers and percentages. Continuous variables will be described with mean, standard deviation, median, quartile 25%, quartile 75%, minimum and maximum.

If baseline confounders, variables that differ statistically and clinically between the randomized groups and known to predict primary outcome variable, are found then complementary analyses will be performed adjusted for these baseline variables.

STATISTISKA KONSULTGRUPPEN		Statistical Analysis Plan	
Protocol:		Protocol No: <protocol number>	
eValuating iDA Selection Ability. The VISA study.		Version: 2.0	Page 16 of 25

All tests will be two-tailed and conducted at 0.05 significance level.

All safety analyses will be descriptive by performed embryo selection method.

All analyses will be performed by using SAS® v9.4 (Cary, NC).

Patient Disposition and Data Sets Analysed

The number of subjects included in each of the ITT, FAS, PP and safety populations will be summarized for each treatment group and overall. The number and percentage of subjects randomized and treated will be presented. Subjects who completed the study and subjects who withdrew from study prematurely will also be presented with a breakdown of the reasons for withdrawal by treatment group for the ITT, FAS, PP and safety populations.

Protocol Violations/Deviations

Major protocol deviations are those that are considered to influence the analysis. A list of protocol deviations that were anticipated before the start of the trial was generated. Once the data collection has been finalized and before database lock the steering committee will review all the possible deviations and if needed create additional categories.

The number of patients with major protocol deviations will be summarized per treatment group.

Demographics and Baseline Characteristics

Demographics and baseline characteristics will be summarized by treatment group for the ITT, FAS and PP populations and analysed according to the methods described in section “General Statistical Methodology” above.

STATISTISKA KONSULTGRUPPEN		Statistical Analysis Plan	
Protocol:		Protocol No: <protocol number>	
eValuating iDA Selection Ability. The VISA study.		Version: 2.0	Page 17 of 25

Main Treatment variables

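### The per-protocol set is settled after the primary outcome is known, with only the randomised group masked, and that mask fails for deviations specific to iDAScore

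*SAP*

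**What the plan says.** **Timing and discretion.** Under Protocol Violations/Deviations in SAP section 5, "A list of protocol deviations that were anticipated before the start of the trial was generated". That list is not reproduced in either document. The same paragraph continues: "Once the data collection has been finalized and before database lock the steering committee will review all the possible deviations and if needed create additional" classes of deviation. The test for a major deviation is a judgement: "Major protocol deviations are those that are considered to influence the analysis".

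**Mask.** SAP 2.1.3 admits to PP all randomised women with no significant violation, analyses them by the selection method actually used, and has the set defined at the clean file meeting "before the database lock without knowledge to which randomised group the patient belongs to". It does not define *significant*. It masks the arm and is silent on outcomes. The steering committee's review in section 5 carries no masking statement of its own.

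**Deviations that show the arm.** The table in protocol 11.2 lists three problems. A missing iDAScore and "Highest scoring embryo overruled" are assigned to the treatment group only; missing embryo pictures can affect both groups. All three are marked as leading to withdrawal of the subject. Protocol 10.4 confines iDAScore to the treatment group after randomisation.

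**Role of PP.** Protocol 14.7 makes PP the primary set and ITT the sensitivity set. The Primary Efficacy Analysis paragraph of the SAP reverses this.

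**The concern.** A PP set is credible only if the decision to exclude a woman cannot depend on whether she became pregnant. There are two usual protections: exclusion rules written in advance, and reviewers who see neither arm nor outcome. Here the written rules are open at two points, namely what counts as significant and which categories may be added late. Of the two masks, only the arm mask is stated, and the wording of an iDAScore-specific deviation defeats it.

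What is at stake under the SAP is the PP analysis as the consistency check on ITT. In a non-inferiority trial readers look to that check, because ITT can be diluted by non-adherence. If PP and ITT agree, or differ, the reader should be able to exclude the possibility that selection explains it.

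**Working it through.** **1. What is known when the review takes place.** SAP section 1 defers live birth and ongoing pregnancy to a later report, and SAP 4.1.3 places live birth at a second database lock. Reading the end of data collection as the end of the initial collection, the review falls after hCG and the primary scan result but before live birth and ongoing pregnancy.

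**2. Whether the arm mask holds.** Two of the three problems in protocol 11.2 occur in one arm only. Day-6 re-scoring and warming in iDAScore order (protocol 10.4, group B) are also confined to that arm, so a deviation in either would reveal it too.

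**3. Where discretion remains.** The two one-arm problems are already marked for withdrawal, so their handling appears pre-set. What is left open is the meaning of *significant* and any category added late. SAP Table 14.1.2, on deviations that lead to exclusion from PP, links the deviation categories to PP membership.

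**4. Reproducing the plan's sample size.** Inputs (protocol 14.5 and SAP sample size section): control rate 0.354; iDAScore rate 0.354 + 0.05 = 0.404; margin 0.05; two-sided 95% CI; power 90%.

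n = (1.960 + 1.282)² × [0.354 × 0.646 + 0.404 × 0.596] / (0.05 + 0.05)² = 10.507 × 0.46947 / 0.01 = 493.3, so 494 per group. The Farrington-Manning formula also gives 494. Then 494 / 0.95 = 520 per group and 1040 in total. The stated figures reproduce.

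**5. Sensitivity of the PP result to selective exclusion.** The lower limit is the Farrington-Manning 95% limit that the SAP specifies, with 494 per arm and 175 control pregnancies (175/494 = 35.4%). For each observed result, k is the smallest number of non-pregnant iDAScore women whose removal brings the limit above -5%.

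| iDAScore pregnancies | Lower limit, no exclusions | k (% of arm) | Lower limit after selective removal of k | Lower limit after outcome-neutral removal of k |
|---|---|---|---|---|
| 165 | -7.93% | 43 (8.7%) | -4.95% | -7.98% |
| 170 | -6.95% | 29 (5.9%) | -4.93% | -7.03% |
| 175 | -5.96% | 14 (2.8%) | -4.99% | -6.01% |
| 177 | -5.56% | 9 (1.8%) | -4.94% | -5.54% |
| 200 (planned +5 points) | -0.99% | 0 | n/a | n/a |

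The 175 row can be checked by hand with the simple Wald limit, which agrees to two decimals:
- No exclusions: difference 0; SE = √(2 × 0.22876 / 494) = 0.03043; limit = -1.96 × 0.03043 = -5.96%.
- After removing 14: 175/480 = 36.46%; difference 1.03 points; SE = √(0.23166 / 480 + 0.22876 / 494) = 0.03075; limit = 1.03 - 6.03 = -4.99% before rounding of the terms.

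**6. Type I error at the margin.** In 20,000 simulated trials with true rates of 30.4% and 35.4%, 494 per arm, the one-sided error of the PP test (nominal 2.5%) was:

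| Women removed from the iDAScore arm | Non-pregnant only | Outcome-neutral |
|---|---|---|
| 0 | 2.1% | n/a |
| 10 | 3.6% | 2.5% |
| 15 | 4.6% | not run |
| 25 | 7.0% | 2.4% |

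**The case against.** The strongest reply is that the plan already has several controls. A list of anticipated deviations predates the trial, and since it is not shown it may already say which deviations exclude. Protocol 9.10 requires deviations to be recorded and analysed in the eCRF as soon as possible, and selection deviations mostly arise before the pregnancy result. Exclusions will be visible in Table 14.1.2 and Listings 16.2.2 and 16.2.3. Adding a deviation category is a separate step from excluding a woman from PP. A review before lock is normal practice.

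Much of this stands. It rules out four stronger readings that a reader might infer:
- *That every outcome is known.* Live birth and ongoing pregnancy come later.
- *That the steering committee writes new exclusion categories.* The SAP speaks of deviation categories; the link to exclusion runs through the PP definition and Table 14.1.2.
- *That the reviewers see outcomes.* This would be an inference from silence. A safeguard is unstated; access is not documented.
- *That the two one-arm problems are themselves open to manipulation.* Both already carry a withdrawal mark.

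The worst case is also deliberately one-sided: every removed woman is a non-pregnant iDAScore patient and no control is removed. It also leaves aside that PP is analysed by actual method, so an iDAScore-arm woman kept in PP after morphology selection would count under morphology.

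What the reply does not meet is the combination. Prompt recording does not settle how a deviation is later classified, public listings do not show whether the outcome influenced that classification, and the one stated mask does not work for iDAScore-specific deviations.

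**Conclusion.** The concern holds in a limited form. The plan leaves room for arm and primary outcome both to be known while PP membership is still partly a matter of judgement. The documents describe an opportunity and give no sign of misuse.

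Its reach is the PP sensitivity analysis. A reader might infer that the trial's main non-inferiority claim is at risk. Under the SAP it is not: ITT is primary, includes everyone randomised, and counts women without a transfer as not pregnant, so this review cannot alter it. The problem would reach the main conclusion only if the PP-primary rule in protocol 14.7 applied. That contradiction with the SAP must be reconciled as a separate matter.

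On size, when the observed rates are close to equal, selective removal of 9 to 14 of 494 women (1.8% to 2.8%) would turn a failed PP result into a pass. Outcome-neutral removal barely moves it, and at the planned +5 points PP passes without any exclusions. All exclusion counts are assumptions, since the documents give no expected number of violations.

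**What to change.** 1. Hold both the steering committee's deviation review and the PP decision at the clean file meeting on a listing with arm, iDAScore fields and outcome fields (hCG, scan, sacs) removed. Show arm-specific deviations under one neutral label, such as *assigned selection method not followed*.
2. State in the SAP which of the anticipated deviations exclude from PP. Include freeze-all women who have not returned three months after the last randomisation: section 5 of the SAP calls them protocol violations without saying whether they leave the PP set.
3. Put any category created after data collection ends into a separate sensitivity PP analysis, leaving the main PP set unchanged.

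The cost is some SAP wording and one masked listing, with no new data or patients. The drawback is that a genuine deviation recognised late stays in the main PP set and is handled only in the additional analysis.

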4.1.1 Demographics and Baseline Characteristics

1. Age (maternal*/paternal), continuous variables.
2. Reason for infertility (couple), categorical variable.
3. Height and weight (mat.), continuous variables
4. BMI (mat.), continuous variable
5. Type of menstruation (mat.), dichotomous variable
6. Number of previous stimulated IVF cycles leading to oocyte pick-up (couple)*, ordered categorical variable (7 categories)
7. Previous pregnancies in current relationship, ordered categorical variable (5 categories)

Treatment variables

1. FSH starting dosage, continuous variable
2. FSH total dosage, continuous variable
3. GnRH downregulation (agonist/ antagonist)
4. Source of sperm, categorical variable (6 categories)
5. Duration of ovarian stimulation, continuous variable.
6. Number of oocytes*, both as continuous variable and ordered categorical variable (7 categories)

STATISTISKA KONSULTGRUPPEN		Statistical Analysis Plan	
Protocol:		Protocol No: <protocol number>	
eValuating iDA Selection Ability. The VISA study.		Version: 2.0	Page 13 of 25

7. Method of fertilization (ICSI/Standard IVF/Combined)* Categorical variable
8. Number of normally fertilized oocytes (2PN)*, continuous variable
9. Number of blastocysts at Gardner Scale 2 or beyond by day 5 (Early blastocysts), continuous variable
10. Proportion of cycles where the embryo selected by the embryologist had the highest iDAScore (Only in the iDAScore group).
11. Number of cryopreserved embryos on day 5 and 6, continuous variable
12. Morphological score of the transferred embryo, continuous variable
13. iDAScore® (treatment group) of the transferred embryo, continuous variable
14. Type (categorical variable) and duration (continuous variable) of luteal phase support

*) These variables are used in a deterministic minimization procedure together with center during randomization. All variables are entered as Categorical variables: Age (5 cat.), number of earlier IVF cycles (7 cat.), number of oocytes (7 categories), fertilization method (3 cat.), number of 2PN oocytes (7 categories) and center (14-15 centers).

Efficacy Variables

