5 STATISTICAL METHODOLOGY

General Statistical Methodology

Primary and all secondary analyses will be performed on ITT population. Complementary analyses will be performed on full analysis set (FAS) and on the per-protocol (PP) population. The primary statistical analyses will be calculation of the mean percentage difference with two-sided 95% confidence interval (CI) regarding the primary efficacy variable Clinical Pregnancy with fetal heartbeat after the first embryo transfer between the iDA group and the trained embryologist (standard) group unadjusted with Farrington-Manning 95% CI. If the lower limit of this 95% CI is larger than -5%, the non-inferiority margin, then non-inferiority is achieved. If non-inferiority is achieved, then we will test primary efficacy variable for superiority with two-sided Fisher's exact test.

Unadjusted and adjusted relative risk (RR) between the two groups with 95% CI will be calculated with Poisson regression model with a robust error variance, (see reference 2) for primary and secondary efficacy variables.

Regarding multiplicity for the primary analysis (clinical pregnancy) and the first two secondary analyses (live birth) and Positive hCG a fixed – sequence test will be applied. (see reference 3)

If non-inferiority is achieved in primary analysis then the probability mass from the primary analysis will be transferred to the first secondary analysis, live birth.

STATISTISKA KONSULTGRUPPEN		Statistical Analysis Plan	
Protocol:		Protocol No: <protocol number>	
eValuating iDA Selection Ability. The VISA study.		Version: 2.0	Page 15 of 25

If non-inferiority is achieved also for live birth then the non-inferiority result for live birth will also be confirmative, and the probability mass will be transferred to the second secondary analysis of positive hCG rate. If non-inferiority is achieved also for positive hCG rate birth, then the non-inferiority results for positive hCG rate will also be confirmative

For the other secondary variables, the p-values will be given for descriptive purpose and no multiplicity adjustment will be performed. These analyses will be considered exploratory.

For unadjusted comparison between the two randomized groups the following tests will be performed: Fisher's exact test for dichotomous variables,

Fisher's non-parametric permutation test for the mean difference between two independent samples for continuous variables,

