Main treatment variables will be summarized by treatment group for the FAS and PP populations and analysed according to the methods described in section “General Statistical Methodology” above.

Efficacy Analyses

Primary Efficacy Analysis

The primary statistical analyses will be calculation of the mean percentage difference with two-sided 95% confidence interval (CI) regarding the primary efficacy variable Clinical Pregnancy with fetal heartbeat after the first embryo transfer between the iDA group and the trained embryologist (standard) group unadjusted with Farrington-Manning 95% CI. If the lower limit of this 95% CI is larger than -5%, the non-inferiority margin, then non-inferiority is achieved. This analysis will be applied on the ITT population (primary) and PP population (sensitivity analysis). Any inconsistencies in these analyses will be discussed in the study report. Unadjusted relative risk (RR) with 95% CI will also be calculated. The Clinical pregnancy rate with exact 95% CI will be calculated for each of the randomised groups.

The following sensitivity analysis will also be performed adjusted for centre and stratification (minimization) variables:

To account for the lack of independence introduced by both the potential clustering within centers and the optimal randomization process (minimization), we will also estimate the difference in the clinical pregnancy probability between the two randomized groups with a 95% CI using a linear mixed effects regression model (with identity link function) with center as a random effect and fixed effects for the following variables used in the randomization:

- Woman’s age:

STATISTISKA KONSULTGRUPPEN		Statistical Analysis Plan	
Protocol:		Protocol No: <protocol number>	
eValuating iDA Selection Ability. The VISA study.		Version: 2.0	Page 18 of 25

< 25; 25 <= Age < 30; 30 <= Age < 35; 35 <= Age < 40; 5. 40 <= Age

- Number of previous stimulated IVF cycles leading to oocyte pick-up

1-5; 6 – 10; 11 – 15; 16 – 20; 21 – 25; 26 ->

- Number of oocytes:

• 2 – 5; 6 – 10; 11 – 15; 16 – 20; 21 - 25; 26 ->

- Fertilization method:

IVF for all; ICSI for all; ICSI for some

- Number of 2PN oocytes

• 2 – 5; 6 – 10; 11 – 15; 16 – 20; 21 - 25; 26 ->

- Center.

Adjustment with centre as random effect, fertilization method as class variable and the other four as continuous variables.

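### The interval that decides non-inferiority ignores the six factors used in the minimisation; it is valid, but the SAP's own adjusted interval would be slightly narrower if those factors predict pregnancy

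*SAP*

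**What the plan says.** The footnote to SAP 4.1.1 describes the allocation: "These variables are used in a deterministic minimization procedure together with center during randomization". The starred variables are maternal age, previous stimulated cycles, oocytes, fertilisation method and 2PN oocytes. With centre, that makes six factors.

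SAP section 5 (General Statistical Methodology, repeated under Primary Efficacy Analysis) makes the deciding analysis the difference in clinical pregnancy rate "between the iDA group and the trained embryologist (standard) group unadjusted with Farrington-Manning 95% CI", on the ITT population. The rule is: "If the lower limit of this 95% CI is larger than -5%, the non-inferiority margin, then non-inferiority is achieved". If it is met, "the probability mass from the primary analysis will be transferred to the first secondary analysis, live birth", and after live birth to positive hCG.

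Primary Efficacy Analysis also specifies an adjusted risk difference, but only as a sensitivity analysis. Its stated reason is "To account for the lack of independence introduced by both the potential clustering within centers and the optimal randomization process (minimization"). The model is a linear mixed model with identity link: "Adjustment with centre as random effect, fertilization method as class variable and the other four as continuous variables". HC3 standard errors are added to allow for non-constant error variance. The SAP's list of tables gives this analysis its own table, 14.2.1.3.

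**The concern.** Minimisation makes the arms more alike on the chosen factors than simple randomisation would. If those factors predict pregnancy, the estimated difference varies less from trial to trial than the unadjusted standard error assumes. The interval is then a little wider than the design warrants. The SAP recognises that the allocation method calls for adjustment, yet lets an interval without adjustment decide.

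One lower confidence limit settles the trial. If it falls below -5 points, the fixed sequence stops before live birth and positive hCG. An interval that is wider than necessary makes that outcome slightly more likely than it need be.

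**Working it through.** **Inputs** (SAP section 1, Sample Size calculation; protocol 14.5): control rate 35.4%; iDAScore rate 40.4%, reading the 5% as percentage points; margin -5 points; two-sided 95% interval; power 90%; 494 per arm; 5% loss; 1040 in total. The documents give no R² (the share of outcome variance that the six factors explain). It is assumed here over 0 to 10%.

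**1. The plan's own figure.** n per arm = (1.95996 + 1.28155)² × (0.354 × 0.646 + 0.404 × 0.596) / (0.05 + 0.05)² = 10.507 × 0.46947 / 0.01 = 493.3, so 494. The Farrington-Manning variance gives 493.7, also 494. Then 988 / 0.95 = 1040. The sizing reproduces.

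Exact enumeration of the unadjusted test:
- 494 per arm: 89.9% power at +5, 37.8% at equal rates, 2.5% one-sided error at -5.
- 520 per arm: 91.5%, 39.1% and 2.5%.

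**2. Width by formula.** At 520 per arm the unadjusted SE is √(0.46947 / 520) = 0.03005, a half-width of 1.96 × 3.005 = 5.89 points. Adjustment multiplies the SE by √[(1 − R²) / (1 − q/N)]. Here q = 6 (four linear terms plus two for fertilisation method) if the random centre effect uses no degrees of freedom, and q = 20 if it uses 14.
- Break-even R² = q/N: 6/1040 = 0.6% to 20/1040 = 1.9%.
- R² = 5%: factor 0.9775 (q = 6) to 0.9842 (q = 20), half-width 5.76 to 5.80 points.
- R² = 10%: factor 0.9514 to 0.9579, half-width 5.60 to 5.64 points.

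**3. Power by simulation.** The formula alone overstates the power gain, because under minimisation the unadjusted estimate already benefits from the balance. At R² = 10% and +5, with N = 1040, its true SD was 0.0287 against a mean Farrington-Manning SE of 0.0301; the adjusted SE was 0.0286. So what changes is the standard error, not the precision of the point estimate.

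Main simulation: N = 988 and 20,000 trials. Assumed: 15 unequal centres; deterministic minimisation with equal weights and a coin toss on ties; prognostic variance split age 60%, centre 15%, 2PN 15%, previous cycles 10%. The table compares unadjusted Farrington-Manning with the SAP's adjusted model (random centre, HC3 per patient).

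| R² | SE ratio, adjusted/unadjusted | Power at +5 (%) | Power at equal rates (%) | One-sided error at -5 (%) |
|---|---|---|---|---|
| 0 | 1.005 | 90.1 → 90.0 | 38.1 → 37.5 | 2.48 → 2.40 |
| 2% | 0.995 | 90.1 → 90.3 | 38.0 → 38.1 | 2.23 → 2.28 |
| 5% | 0.981 | 90.4 → 91.1 | 37.9 → 39.3 | 2.34 → 2.52 |
| 10% | 0.956 | 90.8 → 92.4 | 37.8 → 41.2 | 2.02 → 2.35 |

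Over 988 to 1040 patients, the gain at +5 is 0.5 to 0.8 point at R² = 5% and 1.1 to 1.8 at 10%. At equal rates it is 1.2 to 1.6 and 3.2 to 3.7 points.

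A separately programmed simulation (N = 1040, 9,000 trials per scenario) gave, at +5, unadjusted versus adjusted: 91.3 v 91.0% at R² = 0, 91.6 v 91.5% at 1%, 91.5 v 91.5% at 2%, 91.9 v 92.4% at 5% and 92.0 v 93.3% at 10%. The unadjusted error at the margin was 2.1 to 2.7%, nominal within simulation error.

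The SE therefore breaks even near R² = 1% with random centre, but no power gain is visible until about 1 to 2%. With fixed centre effects the SE is about 1.3% larger at R² = 0 and breaks even at about 2 to 2.5%.

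**The case against.** The case for leaving the plan alone is strong. The unadjusted test holds its error rate and is the test used for the sizing. Any excess width is conservative: it cannot produce a false claim of non-inferiority. The adjusted estimate is already pre-specified and will be reported, so the only question is which of two planned intervals decides. The benefit depends on an R² that nobody has stated, and gains of a full point at +5 appear only towards an assumed 10%. The simulations take age, oocytes and 2PN to act linearly, as the SAP's model does; departures from linearity were not examined and could change the gain. A simple test also leaves less to go wrong than a mixed model.

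All of that stands, and it is why the point is minor. It does not remove the point. The SAP gives the reason for adjusting and has already written the model, the factors are collected for allocation anyway, and the loss if they prove uninformative is small.

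**Conclusion.** The point holds as an optional improvement. The deciding interval is valid and adequately sized at +5. It is slightly too wide if the minimisation factors are prognostic beyond roughly 1 to 2% of the variance. The size rests on the assumed R², on how the prognostic variance is split between factors, and on centre entering as a random effect.

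Four stronger readings are tempting and not supported:
- **That minimisation makes the unadjusted test invalid.** The SAP's remark about lack of independence might suggest so, but the error at the margin stays nominal or slightly below.
- **That the HC3 wording leaves the error rate open.** Variances computed per centre gave one-sided errors of 3.2 to 4.8% in simulation. The SAP names no such estimator. It gives the purpose of HC3 as non-constant error variance, which implies the per-patient form, and that form gave 2.3 to 2.5%.
- **That the category bands undermine the model.** SAP 4.1.1 has "number of earlier IVF cycles (7 cat.), number of oocytes (7 categories), fertilization method (3 cat.), number of 2PN oocytes (7 categories"), while Primary Efficacy Analysis prints six bands for each of the three counts, with previous cycles starting at 1-5. The model enters these variables as continuous, so this is a labelling matter.
- **That adjusting would rescue power at equal rates.** It moves about 38% to about 41% at best over the assumed range.

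**What to change.** Before database lock and while blinded:

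1. Make the SAP's adjusted risk difference the deciding analysis: identity link, random centre, fertilisation method as a class, the other four as continuous, HC3 per patient. Non-inferiority is met if its lower 95% limit exceeds -5 points.
2. Keep unadjusted Farrington-Manning as the sensitivity analysis.
3. Use the same estimator for the live birth and positive hCG non-inferiority steps.
4. Align protocol 14.7 with this choice.

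Two editorial clarifications are useful whichever interval decides: say that HC3 is per patient, and reconcile the category descriptions in SAP 4.1.1 with the bands under Primary Efficacy Analysis. How superiority is tested is a separate matter and is not part of this change.

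**Cost.** Edits to SAP section 5 (including 5.1.1) and protocol 14.7, and a swap of roles between tables 14.2.1.1 and 14.2.1.3. No extra patients or data. If the factors turn out not to be prognostic, the interval is about 0.5% wider and power falls by 0.1 to 0.2 point at +5 and by about 0.5 point at equal rates. The deciding analysis would also no longer exactly match the test used for the sizing.
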